9.10. Sponsor

North Bristol NHS Trust will act as the Sponsor for this trial. Delegated responsibilities will be assigned to the NHS trusts taking part in this trial.

9.11. Monitoring

The study may be subject to inspection and audit by North Bristol NHS Trust (under their remit as sponsor) and other regulatory bodies to ensure adherence to GCP and the NHS Research Governance Framework for Health and Social Care (2nd edition).

9.12. Patient expenses

No incentive payment will be made to patients for participation in the trial. However, the study will reimburse (upon production of receipts where appropriate) all reasonable travel expenses incurred by patients for follow-up visits which are outside of standard care (e.g. travel for early follow up appointments or semi-structured interviews).

10. DATA MANAGEMENT

10.1. Data Recording, Storage and Access

Accurate and contemporaneous source data will be kept for all trial participants. This will typically comprise the standard demographic information, past medical history, results from haematological biochemical, microbiological and radiological investigations.

All data will be stored securely in line with the Data Protection Act and the principles of the GCP. Electronic data will be stored on encrypted and password-protected servers. Physical records will be stored securely in the Clinical Research Centre (CRC) within North Bristol NHS Trust, with access limited to members of research teams only.

The trial database will be built using the REDCap database management software. Trial data will be captured using case report forms (eCRF), which will be completed by the trial team. The trial database will only be accessible to named personnel within the trial team using the password-protected REDCap website.

The semi-structured interview data will be audio-recorded using a specified voice recorder. These recordings will then be uploaded and stored on password-protected and encrypted NHS servers which are owned and managed by the Sponsor.

For the purposes of analysis, semi-structured interview recordings will be transcribed and anonymised. This will be performed by The Transcription Company (Sutton Coldfield, West Midlands, <http://www.thetranscription.co.uk/security-confidentiality-statement/>), who are approved by the University of Bristol. All data transfer and storage will be performed in line with the rules stipulated by the Data Protection Act (2018) by the University of Bristol.

10.2. Missing Data and Data Queries

Data queries will be automatically generated by the trial database at the time of data entry. The database will only be locked (allowing final analysis to begin) once the Trial Steering Committee is satisfied that all data queries have been addressed as completely as possible. Missing data will be minimised by maintaining contact with participants (to avoid missed appointments), and by completing eCRFs using notes reviews or telephone contact if necessary (where appropriate consents are in place).

10.3. Data Monitoring

The trial may be monitored by the Sponsor or other regulatory bodies. For the purposes of audit and compliance monitoring, clinical trial data will be available to delegated members of the local trial teams, as well as to representatives of the Sponsor, relevant regulatory authorities, and the trial co-ordinating team. Participants will consent to their trial data being released for this purpose.

10.4. Publication Policy

The Trial Management Group will have sole responsibility for the expedient preparation, review and submission of any manuscripts, abstracts, press releases or other publications detailing the trial's procedures or findings. Any publication will include a list of investigators, with authors being determined in line with the ICMJE guidelines, as well as an acknowledgement of roles of the trial Sponsor and Funder(s).

11. STUDY MANAGEMENT

[figure not shown]
11.1. Trial management group (TMG)

The TMG is responsible for the day-to-day management of the study. It is responsible for all aspects of the trial, including budget management; protocol compliance; and ensuring the immediate safety of trial participants. The TMG will consist of the Sub Investigator, Chief Investigator, and the lead trial nurse. The TMG will report to the Trial Steering Committee at regular intervals.

11.2. Trial Steering Committee (TSC)

The role of the TSC is to provide overall direction and supervision for the trial, as well as to monitor its progress and its adherence to the necessary regulations. It will meet regularly to discuss the trial's progress. It comprises both researchers working on the study and independent physicians, as well as both lay and medical members. The TSC members will include the members of the TMG, along with an independent Chairperson, two key investigators; an independent lay (patient) member; and an independent physician expert.

APPENDIX 1; ACTION TRIAL FLOWCHART

APPENDIX 2; TRIAL INTERVENTION SUMMARY TABLE

Timepoint	Events	Duration	Activities
Pre-enrolment	Screening and pre-screening	10 mins	Complete screening log for all patients with pleural infection Provide patient information sheet A where applicable (ACTion trial) Provide patient information sheet B (semi-structured interview)
Enrolment	Trial consent	30 mins	Complete consent form A (Trial consent)
Baseline assessment	Baseline assessment	60 mins	Baseline CRF HRQoL questionnaire and VAS Thoracic ultrasound scan Bloods if not performed within previous 24 hours Chest x-ray if not performed within the previous two days
Randomisation	Randomisation and treatment allocation	10 mins	Access REDCap randomisation system and input required information Inform patient and necessary staff of treatment allocation
Intervention arm	Therapeutic thoracentesis	60 mins	Appropriate procedural consent Therapeutic thoracentesis using Rocket aspiration kit- aspirate largest collection of fluid to dryness or until symptoms of trapped lung. Chest radiograph within 12 hours of procedure end
Control arm	Chest tube insertion	60 mins	Appropriate procedural consent Seldinger chest tube (12 or 18F) Chest radiograph within 12 hours of procedure end
Inpatient period	Inpatient assessments	30 mins each	At least alternate day bloods until day 7 post randomisation Thoracic ultrasound on days 3 and 7 (if working days) Chest radiograph on days 3 and 7 (if working days) and after pleural procedures including chest tube removal Clinical assessments as part of standard care HRQoL questionnaire and VAS on days 3 and 7 days (if working days) then every 7 days till discharge
Discharge from admitting hospital	Discharge assessment	30 mins	Discharge CRF including HRQoL questionnaire and VAS Arrange date for semi-structured interview if applicable

Early outpatient assessments	Outpatient assessment	60 mins	Bloods if not performed within 48 hours Clinical assessment Thoracic ultrasound Repeat therapeutic thoracentesis if necessary Consideration for cessation of outpatient assessments or re-admission to hospital
Day 30 post randomisation (+/- 5 days)	Semi-structured interviews	60 mins	HRQoL questionnaire and VAS Complete consent form for semi-structured interviews (Consent form B) Semi-structured interview (patient's home, clinic or hospital)

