2.5. Assessment and management of risk

Pleural infection has the potential to be a serious and potentially fatal condition. Recent longitudinal data has shown the mortality in all cases is around 5% when managed conventionally. Patients at higher risk of mortality or adverse events could be anticipated using a recently developed prognostication tool called the RAPID score. This study will collect the data needed to perform a RAPID score and it will form part of the consideration for hospital discharge and early follow up. Subsequent morbidity from pleural infection is poorly understood, even following standard care.

Therapeutic thoracentesis is a frequently performed intervention in the management of pleural fluid. It is a relatively straightforward procedure and is part of the mandatory curriculum for UK core medical trainees. The case series data for TT in pleura infection is limited to 165 patients across 3 non-comparative studies but these have not shown adverse outcomes compared to normal practice.

Within the ACTion trial participant safety will be guaranteed by regular clinical and radiological review. Participants will have radiological assessment using ultrasound and chest radiograph at baseline (Day 1), Day 3 and Day 7 as a minimum. Whilst an inpatient, participants will have daily review from a physician and their clinical and radiological status will dictate the requirement for further procedures, intrapleural fibrinolytics or surgical referral. Once a participant is felt to be well enough to be discharged from hospital, their current clinical status will dictate the requirement for outpatient follow up. It is anticipated that some patients may require more intensive outpatient

follow up initially. All patients will be reviewed in pleural outpatient clinic at 3 months as part of standard care.

A trial steering committee (TSC) will meet on 3 separate occasions throughout the trial period (3, 6, 12 months). There will be a PPI representative on the TSC, and the role of the committee is to ensure concordance with the protocol and to ensure it remains safe and patient centred.

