5.7. Post procedure inpatient period

All patients

Whilst in hospital, all patients will have a clinical review on every working day. As a minimum a chest radiograph will be performed on Day 3 (+/- 1 day) and Day 7 (+/- 1 day), with additional as deemed necessary by the treating physician.

Blood tests should be performed on at least alternate days until day 7, and then at least weekly if the patient remains in hospital.

Thoracic ultrasounds should be performed on day 2 (the day after the first procedure), and then on days 3 (+/- 1 day) and 7 (+/- 1 day), with additional performed as deemed necessary by the treating physician.

Discharge from hospital is ultimately at the discretion of the treating physician. Numerous factors form the basis of this decision to the extent it becomes impossible to protocolise. It is assumed that

as part of good clinical care all aspects of a patient's condition will be assessed before discharge, including clinical status, outpatient follow up and social set up

Control groups

The timing for chest tube removal in the control group is at the discretion of the treating physician. If the chest tube is removed, the patient should have a chest radiograph afterwards.

Interventional group

There may be a requirement for patients to have further therapeutic aspirations if there is reaccumulation of infected pleural fluid. This is an anticipated drawback of this approach and will be explained to the patients as part of the randomisation process. The need for a timing of further procedures will be decided by the treating physician. It is advised they consider the following before making a decision

- clinical/biochemical factors (such as rising CRP/WBC, or fevers).
- Chest radiograph appearances suggesting persisting collections
- Pleural ultrasound appearances suggesting persisting collections as well as the amenability of these collections to drainage

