6.2. Imaging

Thoracic Ultrasound

All pleural ultrasounds will be performed as part of standard care. The scan results from the baseline assessment, third (+/- 1 day) and seventh (+/- 1 day) days should be recorded on the electronic trial database. Additionally, the results prior to any pleural procedure that are additional to the above should be recorded as they form part of the reasoning for additional pleural procedures. A pleural ultrasound should also be performed and recorded at the trial follow-ups (Day 30 and 90).

Scans should be performed by those with at least Royal College of Radiologists Level One accreditation (or equivalent).

Chest radiography

All chest radiographs performed during the ACTion trial are part of standard care. Images should ideally be performed as P-A. Whilst an inpatient, chest radiographs should be performed on Day 3 and Day 7, with additional as deemed necessary by the treating physician. They will also be performed after every pleural procedure as part of standard care (including chest tube removal), as well as on trial follow-ups (Day 30 and 90). Given the intervention arm may result in patients having additional pleural procedures there may be an increased number of chest radiographs required in this group. However, the exact number of additional pleural procedures is difficult to predict and forms part of the trial outcomes.

The size of effusion on chest radiograph will be reported by a clinical member of the research team and recorded in the online database.

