6.3. Health related quality of life questionnaires

All patients will be asked to fill in an EQ-5D questionnaire and a VAS scoresheet for chest pain and breathlessness. These assessments will take place at baseline (Day 1), Day 3 (+/- 1 day), Day 7 (+/- 1 day) and at the trial follow ups (day 30 and 90).

EQ-5D

The EQ-5D is a 5 domain (paper-based or electronic) questionnaire which gives an overall assessment of an individual's quality of life at a particular timepoint. There are 5 questions and it is envisaged this should take between 1-2 minutes to complete.

VAS score

The ACTion trial is using a VAS score instrument to record patients reported chest pain and shortness of breath. The patient will be asked to mark on a line scale their assessment of their symptoms at that time. This should take around 30 seconds per scale.

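### Section 6.3 asks all patients for EQ-5D and VAS at Day 7, but Appendix 2 lists those forms for inpatients only, and no Day 7 route is set for patients discharged before Day 6

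*Protocol*

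**What the plan says.** On the questionnaires, section 6.3 is unconditional: "All patients will be asked to fill in an EQ-5D questionnaire and a VAS scoresheet for chest pain and breathlessness". It continues: "These assessments will take place at baseline (Day 1), Day 3 (+/- 1 day), Day 7 (+/- 1 day"), followed by Days 30 and 90. Nothing there restricts the early forms to inpatients.

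Appendix 2 is narrower. In its inpatient row it lists "HRQoL questionnaire and VAS on days 3 and 7 days (if working days) then every 7 days till discharge". The discharge row adds one EQ-5D and VAS on the day the patient leaves. The early outpatient row lists bloods, clinical assessment and ultrasound, but no EQ-5D or VAS and no fixed day.

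Imaging shows a similar mismatch. Section 2.5 says "Participants will have radiological assessment using ultrasound and chest radiograph at baseline (Day 1), Day 3 and Day 7 as a minimum". Section 6.2 ties the radiographs to the stay ("Whilst an inpatient, chest radiographs should be performed on Day 3 and Day 7"), 5.7 places the imaging under an inpatient heading, and Appendix 2 has "Thoracic ultrasound on days 3 and 7 (if working days") in the inpatient row. Section 2.5 also says that once a patient is fit for discharge, "their current clinical status will dictate the requirement for outpatient follow up".

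**The concern.** Section 3.3 makes EQ-5D and the VAS for chest pain and breathlessness secondary outcomes, and describes these outcomes as possible primary outcomes for a full-scale trial. Section 7.3 wants measures of variation, and data completion including differences between arms, in order to design that trial.

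If the table is what staff work from, whether a Day 7 value exists depends on still being in hospital. Length of stay is what thoracentesis is meant to shorten (2.4, 9.3), and 5.8 says its patients may leave before the infection has fully resolved. Control patients stay at least while the tube is in, usually 3-5 days (2.7). Day 7 values would then describe slower recoverers, possibly a different slice in each arm. Completion by arm would also depend on which section supplies the denominator. An analysis plan cannot recover forms that were never handed out.

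**Working it through.** **1. Where the gap begins.** Day 7 within one day is Days 6 to 8. A discharge form falls in that window only if discharge is on Days 6-8. A patient discharged on Day 5 or earlier leaves before it opens.

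**2. What could fill it after discharge.**

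| Provision | Covers Day 7 EQ-5D and VAS? |
|---|---|
| Discharge form (Appendix 2) | No, dated before the window |
| Early outpatient visit (5.8, Appendix 2) | No: discretionary, undated, no EQ-5D or VAS listed |
| Postal and phone fallback (5.12) | No, tied to the Day 30 and Day 90 visits |
| Telephone completion of eCRFs (10.2) | Possible for EQ-5D; sets no Day 7 contact and does not suit a VAS marked on a line |

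**3. Day 3 is largely safe.** A discharge form on Days 2-4 falls in the Day 3 window, and a patient leaving on Day 5 was in hospital throughout it.

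**4. How many patients.** The protocol gives no distribution of discharge day. It gives median stays of 7 and 10 days for low- and medium-risk patients (2.3) and an average of 13 days (2.1), used here as a median. The rest is assumed:
- stays are lognormal with log-SD 0.5 to 0.7 and run from Day 1;
- presence on Day 6 means a stay of at least t = 5 or t = 6 days, the two ways of counting Day 1;
- thoracentesis shortens the median by 0%, or by 25% to 50%;
- there are 15 patients per arm.

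Formula: P(stay ≥ t) = Φ(ln(median/t)/log-SD). Over t and log-SD:

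| Control median | Control in hospital on Day 6 | Thoracentesis, 25-50% shorter | Out before Day 6, no shortening (of 30) | Out before Day 6, 25-50% shorter (of 30) | Arm difference in forms (of 15), 25-50% shorter |
|---|---|---|---|---|---|
| 7 days | 0.59-0.75 | 0.14-0.54 | 7.5-12.4 | 10.7-18.6 | 2.4-7.7 |
| 10 days | 0.77-0.92 | 0.36-0.79 | 2.5-7.0 | 4.4-12.5 | 1.8-7.3 |
| 13 days | 0.87-0.97 | 0.55-0.91 | 0.8-4.0 | 1.8-8.8 | 0.9-5.6 |

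For the highest no-shortening figure (median 7, t = 6, log-SD 0.7): ln(7/6)/0.7 = 0.220, Φ = 0.587, and 30 × (1 − 0.587) = 12.4. With no shortening the arm difference is 0.

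**5. Effect on completion.** Take median 10, 25% shortening, log-SD 0.5 and t = 6. Control: Φ(ln(10/6)/0.5) = 0.847, or 12.7 of 15. Thoracentesis: Φ(ln(7.5/6)/0.5) = 0.672, or 10.1 of 15. If every form due under Appendix 2 is returned, completion is 100% in both arms by the table and 85% against 67% by 6.3.

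**6. The working-day condition.** Days 2-4 and Days 6-8 are each three consecutive days, so each contains at least one weekday. With the window in 6.3 applied, the condition costs nothing.

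**The case against.** The strongest reply is that 6.3 already schedules the Day 7 forms for everyone. Appendix 2 is a summary table, and 10.2 allows forms to be completed by telephone across the trial. A reader might infer that discharged patients have no Day 7 assessment in the protocol at all. The documents do not support that: the assessment is stated, but the table contradicts it and no means of collection is given. The conflict stands, because 10.2 fixes no contact at Day 7.

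A reader might also infer that Day 7 imaging data needed for an outcome would be lost. No outcome in 3.3 uses them; the radiographic outcome compares Day 90 with baseline. Radiographs follow every procedure, and 5.7 adds an early scan for those in hospital ("Thoracic ultrasounds should be performed on day 2 (the day after the first procedure")). The imaging mismatch is one of wording. Likewise, the working-day condition might be read as losing every form that falls on a weekend, but the one-day window absorbs this.

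Unequal loss by arm is not established. The one prospective study cited in 2.2, paediatric and non-randomised, found no significant difference in stay. Thoracentesis patients may receive a chest tube for fibrinolytics (5.10), and some control patients would also leave before Day 6. Baseline, discharge, Day 30 and Day 90 forms remain, and analysis is descriptive. All of this limits the consequence without removing it. The discharge form does not replace a Day 7 value, because its date is itself set by length of stay.

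**Conclusion.** The point holds for EQ-5D and VAS at Day 7 in patients discharged before Day 6: two sections conflict and no collection mechanism is set. This rests on the text alone. The numbers rest on the assumed stay distribution and on counting stay from Day 1. On those assumptions about 1-12 of 30 patients are affected if stay is not shortened, with no difference between arms, and about 2-19 of 30 if thoracentesis shortens stay by 25-50%, with about 1 to 8 fewer forms in that arm. Selective loss by arm is therefore probable only if stay is shortened. The ambiguous completion denominator does not depend on an arm difference. The primary outcome, uptake of randomisation among eligible patients, is unaffected. This is worth correcting because the data concerned are meant to inform the full trial.

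**What to change.** - State in 6.3 and Appendix 2 that EQ-5D and VAS at Day 3 and Day 7, each within one day, are due for every participant alive and not withdrawn, in hospital or not.
- Give dated paper forms at discharge for postal return, with a phone reminder. Paper is needed for the VAS.
- Let the discharge form count when it falls inside a window.
- In Appendix 2, replace the working-day condition with the one-day window already in 5.7 and 6.3.
- Use the same denominator for completion in 7.3.
- For imaging, only reword 2.5 so that the Day 3 and Day 7 minimum applies to inpatients, in line with 5.7 and 6.2. Do not add outpatient Day 7 imaging: the early outpatient row lists no radiograph, and since 5.8 expects those visits more often after thoracentesis, the additions would fall mostly in that arm.

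The cost is wording in 2.5, 6.3, 7.3 and Appendix 2, plus Day 7 forms to chase by post or phone: about 1 to 19 of 30 across all the assumptions above. No visit or radiograph is added.
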